7.3. Randomization

Although we had considered using an Urn randomization (Stout et al., 1994), we ultimately decided against this since extensive moderator tests in the parent R01 were negative with one exception; i.e., level of baseline trait anxiety. Although only about 11% of cases were below the threshold cut-off for clinically significant trait anxiety, this status interacted with group assignment such that CBT was less effective in this small group. Therefore, we will utilize a permuted-block randomization scheme with stratification on this variable. This should result in the approximate 33 cases below the clinical threshold being distributed evenly across the three groups. (Note we had considered that the anxiety disorder of these low trait anxiety cases could be mis-diagnosed but an inspection of the parent R01 data suggest they are typically cases whose anxiety response is triggered in very specific circumstances so trait anxiety can be lower.)

7.4. Descriptive analyses

To confirm that the randomization scheme achieved the intended aim of evenly distributing important study characteristics, groups will be statistically compared on baseline demographic and clinical variables. Any significant group differences on these baseline variables would be factored into study analyses (e.g., using covariates).

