6.4.1 Interviews/Diagnoses

a). Structured Clinical Interview for DSM IV (SCID). (45 minutes) Selected modules from the SCID to determine diagnostic status with reference to anxiety disorders, depression and alcohol/drug use disorders. The SCID is essentially a checklist of psychiatric diagnostic criteria (i.e., symptoms and problems) that are rated by the interviewer as "present," "absent" or "sub-clinical" or "in-determinant." This is administered at the follow-up appointments of the study.

b) Timeline Follow-Back (TLFB). (15 minutes) The TLFB interview will be used in all primary assessment to identify daily drinking patterns of patients in the four months before treatment and in the intervals between study assessments. Using a calendar, the respondent provides retrospective estimates of daily drinking over a specified amount of time.

6.4.2 Questionnaire Packets (1 to 1.5 hours) (Each questionnaire takes about 5 minutes to complete and typically includes 20 multiple choice questions or less) (References and rationale for questionnaires are provided below).

a) Anxiety.

- State-Trait Anxiety Inventory (STAI)
- Penn State Worry Questionnaire (PSWQ)
- Beck Depression Inventory (BDI)
- Panic Disorder Severity Scale (PDSS)
- Social Phobia Scale (SPS)
- Inventory of Depression and Anxiety Symptoms (IDAS)
- Perceived Stress Scale (PSS)

b) Alcohol.

- Alcohol Expectancy Questionnaire (AEQ)
- Inventory of Drinking Situation (IDS)
- Situational Confidence Questionnaire (SCQ)
- Obsessive-Compulsive Drinking Scale (OCDS)
- Addiction Severity Index (ASI)
- Reasons for Drinking Questionnaire (RFDQ).
 - Drinking to Cope Questionnaire (DCQ)
 - Negative Emotions and Use Questionnaire (NEUQ)

c) Other

- Demographics
- Treatment Services Summary (TSS)
- Suicidality Questionnaire (SQ)
- Personality Inventory for DSM-5 Brief Form (PID-5)

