7.5. Primary Aim: To compare the CBT-DC and CBT-AR groups on alcohol outcomes

We predict that the CBT-DC group will have superior alcohol outcomes compared to the CBT-AR group. The primary intention to treat (ITT) population will include all patients randomized. The per-protocol (PP) population will include patients who completed at least four of six (66%) of the therapy sessions with CBT-O patients not missing any more than one of the three AR or DC content sessions. Hypotheses based on the vicious cycle model and parent R01 findings suggest that without alcohol-anxiety de-coupling therapy, drinking relapse is more likely to occur and more severe when it does occur. Therefore, we consider as primary outcomes both categorical relapse status (yes vs. no) and continuously measurement of relapse severity (percent/number days drinking and drinks per drinking day). Secondary alcohol outcomes tested include categorical status on: a) alcohol dependence (yes vs. no) and hazardous drinking (yes vs. no). Follow-up assessments occur 1-, 4- and 8-months following the conclusion of the study therapy and are keyed to the time since the last assessment. To align study findings with the parent R01, the primary assessment point will be the 4-month FU. However, hypotheses will also be tested across all time points to establish temporal patterns of group effects. We test the hypotheses using mixed effects models if data residuals are

normally distributed and generalized estimating equations (GEE) if the data are non-normally distributed (Gueorguieva, & Krystal, 2004; Liang & Zeger, 1986). Both are flexible regression methods for incomplete repeated measures data and allow continuous and categorical covariates, fixed and time-dependent covariates, and a specification of unstructured as well as structured covariance matrix. Categorical outcomes will be evaluated using chi-square tests of proportions and logistic regression, with statistical significance criterion also set at $p < 0.05$. Zero-inflated negative binomial analyses will be used to contrast the study groups on count variables if warranted by a high percentage of zero alcohol use days over the follow-up (e.g., Agresti, 2002).

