The principal power estimate focuses on categorical analyses since these will provide the most conservative power estimates and because we have somewhat more information available to estimate these outcomes for the Primary Aim study groups. (ES for continuous/count alcohol outcomes all demonstrated larger group effects than the categorical outcomes in the parent R01 [Kushner et al. 2013-a].) The best estimate for the categorical CBT-AR alcohol outcome comes from the PMRT group (also devoted exclusively to anxiety reduction) in the parent R01 (i.e., 53% relapse at four months). The parent R01 does not provide a point estimate for the CBT-DC group relapse rate but our prediction that the CBT-DC group will ameliorate all (or most) of the deleterious effect on recovery conferred by a co-occurring anxiety disorder allows us to place this estimate at 21%; i.e., the relapse rate at four months of an AUD treatment group with no co-occurring anxiety disorder (Kushner et al., 2005; also see Driessen et al., 2001 for similar estimates). These estimated results would represent a large effect size ($OR = 4.2$), which would require a sample of only 41 per group to identify an effect at an $\alpha = .05$ level with 80% power; however, a larger sample size would be required to identify other predicted effects with the same power. Further, we cannot be certain that our empirically- and theoretically-informed prediction that the CBT-DC will mitigate all/most of the risk for relapse conferred by co-occurring anxiety disorder is correct until the study is conducted. Therefore, we also calculated a minimum detectable ES showing that we could detect an OR as small as 2.3 with 80% power in the planned sample size using a two-tailed test and 0.05 alpha-level. Although we would be at a higher risk of missing effects even smaller than this, such negative findings would not constitute a meaningful Type II error because they would be of increasingly trivial clinical importance (e.g., Ferguson, 2009). **Therefore, the Primary Aim will be put to a meaningful and scientifically valid test under a wide range of clinically meaningful effect sizes.**

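### Covariates are to be chosen by baseline significance tests, and neither the stratification factor nor baseline drinking is named in any model

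*Combined protocol and SAP*

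**What the plan says.** Section 7.4 compares the groups statistically on baseline demographic and clinical variables. It does not list the variables, give an alpha, or say whether the tests are three-group or pairwise. It then says: "Any significant group differences on these baseline variables would be factored into study analyses (e.g., using covariates"). No other rule for choosing covariates appears in the documents.

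Section 7.3 explains that baseline trait anxiety was the one positive moderator in the parent trial and concludes: "we will utilize a permuted-block randomization scheme with stratification on this variable". About 33 patients are expected below the clinical threshold.

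Baseline drinking is measured. Section 6.4.1 states: "The TLFB interview will be used in all primary assessment to identify daily drinking patterns of patients in the four months before treatment". Section 6.8.3 derives all alcohol outcomes except alcohol dependence from the same interview, the Timeline Follow-Back (TLFB).

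Section 7.5 says that mixed models and GEE "allow continuous and categorical covariates, fixed and time-dependent covariates", which describes what the methods can do and specifies no model. For the other outcome types it says "Categorical outcomes will be evaluated using chi-square tests of proportions and logistic regression" and, if zeros are frequent, "Zero-inflated negative binomial analyses will be used to contrast the study groups on count variables". Sections 7.5 to 7.8 never name the trait-anxiety stratum or baseline TLFB drinking as a model term.

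**The concern.** Under valid randomisation the groups differ at baseline only by chance. A significance test therefore says nothing about whether a variable predicts drinking at follow-up, which is the reason to adjust for it. A strongly prognostic variable is left out in nearly every trial, and an irrelevant one gets in whenever chance happens to flag it.

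Two omissions follow. The stratification factor is balanced by design, so the rule passes over the one variable that the design singled out. Baseline drinking is left without a role: 7.5 does not say whether it is a covariate, the first row of the outcome vector, or unused.

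What is at stake is precision for smaller effects and for the continuous drinking outcomes, together with an adjustment set that cannot be known in advance. With no variable list, no alpha and only an example of the method, two analysts could follow 7.4 and fit different models.

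**Working it through.** **Inputs from the plan.** Relapse 53% (CBT-AR), 21% (CBT-DC) and 41% (CBT-O), from 7.5 and 7.6; two-sided alpha 0.05 and a minimum detectable odds ratio of 2.3 (7.5); 100 per group and 0.40 SD (7.8, where it powers the mechanism measures); about 11% below the trait-anxiety threshold (7.3).

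**Assumed, because the plan gives no figure.** Prognostic strength of baseline drinking, the number of baseline tests, and the block size.

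**1. The plan's own figures.** With pooled variance, n = [1.96·√(2p̄(1−p̄)) + 0.84·√(p₁(1−p₁)+p₂(1−p₂))]² / (p₁−p₂)². The continuity correction is n′ = (n/4)·[1+√(1+4/(n|p₁−p₂|))]².
- 53% vs 21%: n = 34.5, n′ = 40.5, so 41 per group, as stated.
- 41% vs 21%: n = 82.8, n′ = 92.5, so 93 per group against the stated 94.
- 0.40 SD at 100 per group: power about 80%, as stated.

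The concern changes none of these.

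**2. How often the rule admits a variable.** A null baseline variable is flagged in 5% of trials by one three-group test at 0.05, or in about 12% if any of three pairwise tests counts. With k independent tests, P(at least one flag) = 1 − 0.95ᵏ: 23% (k=5), 40% (k=10), 64% (k=20). Correlated scales lower these figures. For the stratum (300 patients, 11% low, blocks of 3, 6, 9 or 12 within stratum), a three-group chi-square test reached p<0.05 in 0 of 20,000 simulated trials at each block size.

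**3. Relapse, 100 per group.** Exact chi-square power is 0.998 at 53% vs 21%. The plan's fallback is that "we could detect an OR as small as 2.3 with 80% power in the planned sample size". From 53%, that odds ratio gives odds of (0.53/0.47)/2.3 = 0.490, or 32.9%, and exact power is 0.832. At 41% vs 21% it is 0.874. The next table comes from simulation, 10,000 trials per setting.

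| Contrast | Method | OR per SD 1.0 | 1.5 | 2.0 | 2.5 |
|---|---|---|---|---|---|
| 53% vs 32.9% | chi-square | 0.836 | 0.835 | 0.837 | 0.831 |
| | 7.4 rule | 0.835 | 0.836 | 0.840 | 0.837 |
| | pre-specified logistic | 0.830 | 0.838 | 0.860 | 0.876 |
| 41% vs 21% | chi-square | 0.871 | 0.878 | 0.878 | 0.875 |
| | 7.4 rule | 0.870 | 0.878 | 0.880 | 0.880 |
| | pre-specified logistic | 0.867 | 0.883 | 0.900 | 0.913 |

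At 53% vs 21% every method gives 0.997 or more.

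**4. Normal continuous outcome, 100 per group, d = 0.40.** Adjusting for a baseline with correlation r multiplies the residual variance by 1−r², so the noncentrality is 0.40/√(2/100)/√(1−r²). Unadjusted, this is 2.83 and power is 0.804.

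| Assumed r | 0.1 | 0.2 | 0.3 | 0.5 |
|---|---|---|---|---|
| Pre-specified covariate | 0.808 | 0.819 | 0.839 | 0.90 |
| 7.4 rule (20,000 simulated trials) | 0.806 | 0.804 | 0.809 | 0.815 |
| 7.4 rule under the null | 0.051 | 0.047 | 0.047 | 0.043 |

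The rule does not inflate type I error, and it recovers very little of the available precision. The way baseline enters also matters: a change-from-baseline contrast with equal variances would give 0.555, 0.605, 0.662 and 0.804 at the same correlations. The plan does not say that it uses one.

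No figure is offered for zero-inflated models.

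**The case against.** The best defence is that little is lost. The planned primary relapse contrast gains nothing, no sample size moves, and the selection uses baseline data only, so it cannot be steered by outcomes. The documents give no evidence that baseline drinking is prognostic; if it is weak, the gain is about a point or less. This stands, and it limits the size of the finding.

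The 0.40 SD is also borrowed from the mechanism measures. Section 4.3 reports parent-trial alcohol effects of d = 0.42 (drinking days), 0.48 (binge days) and 0.68 (drinks per month). Treated as normal outcomes, which is approximate, these give unadjusted power of 84%, 92% and 99.8%. The gains at r = 0.5 are about 9, 5 and 0 points. The gain therefore shrinks for the larger effects but is nearly the same for drinking days.

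The 5% entry rate holds for a three-group test or any single contrast; with three pairwise tests it is about 12%. Either way the selection is by chance.

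On the remedy, an adjusted relapse test moves the headline odds ratio to a conditional scale, while 7.5 wants alignment with the parent study. Chi-square cannot adjust, however, so a regression is needed, and the unadjusted result can be kept as supportive. With about 22 low-anxiety patients in any two-group contrast, a zero-inflated model with the stratum in both parts might fail to fit. A small check found little difference (5 versus 3 failures in 40 fits), but a stated fallback is sensible.

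**Conclusion.** The concern holds. The only covariate rule selects on chance imbalance, and the adjustment set is not pre-specified. This should be corrected, although it does not threaten the trial's validity.

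The loss is nil at 53% vs 21%. It is about 0 to 5 points of power at an odds ratio of 2.3, and about 0 to 4 points for the Secondary Aim. For a normal outcome at 0.40 SD, pre-specified adjustment gains under 1 point at r = 0.1 and about 10 points at r = 0.5. These ranges rest on assumed prognostic strength and 100 patients per group. The smaller effects matter because 7.5 itself says that the 21% rate is uncertain, and because it makes days drinking and drinks per drinking day primary outcomes.

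The stratum adds little precision. Its place in the model is to match the analysis to the stratified randomisation, and as a main effect it does not address the moderation seen in the parent trial.

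**What to change.** Replace the rule in 7.4 with pre-specified adjustment, in every regression model for the Primary, Secondary and Tertiary Aims, for (1) the trait-anxiety stratum and (2) baseline TLFB drinking.

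- Enter baseline drinking as a covariate and keep only follow-up values in the outcome vector.
- For each continuous or count outcome, use the matching baseline measure.
- For relapse, use baseline percent drinking days. Alcohol use in the preceding 30 days is an inclusion criterion (6.3.3), so baseline any-use is constant.
- In a zero-inflated model, put both covariates in the count part and the zero part, and state in advance what is done if the fit fails.
- Name the adjusted logistic regression as the primary relapse test and state that its odds ratio is conditional. Keep the unadjusted proportions and chi-square as supportive, for comparison with the parent study.
- Report the baseline table descriptively, without tests.

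The cost is SAP text only, since both covariates are collected before randomisation. The one drawback is that the conditional odds ratio is not directly comparable with the parent study's unadjusted result, which the supportive analysis covers.

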7.5. Primary Aim: To compare the CBT-DC and CBT-AR groups on alcohol outcomes

We predict that the CBT-DC group will have superior alcohol outcomes compared to the CBT-AR group. The primary intention to treat (ITT) population will include all patients randomized. The per-protocol (PP) population will include patients who completed at least four of six (66%) of the therapy sessions with CBT-O patients not missing any more than one of the three AR or DC content sessions. Hypotheses based on the vicious cycle model and parent R01 findings suggest that without alcohol-anxiety de-coupling therapy, drinking relapse is more likely to occur and more severe when it does occur. Therefore, we consider as primary outcomes both categorical relapse status (yes vs. no) and continuously measurement of relapse severity (percent/number days drinking and drinks per drinking day). Secondary alcohol outcomes tested include categorical status on: a) alcohol dependence (yes vs. no) and hazardous drinking (yes vs. no). Follow-up assessments occur 1-, 4- and 8-months following the conclusion of the study therapy and are keyed to the time since the last assessment. To align study findings with the parent R01, the primary assessment point will be the 4-month FU. However, hypotheses will also be tested across all time points to establish temporal patterns of group effects. We test the hypotheses using mixed effects models if data residuals are

normally distributed and generalized estimating equations (GEE) if the data are non-normally distributed (Gueorguieva, & Krystal, 2004; Liang & Zeger, 1986). Both are flexible regression methods for incomplete repeated measures data and allow continuous and categorical covariates, fixed and time-dependent covariates, and a specification of unstructured as well as structured covariance matrix. Categorical outcomes will be evaluated using chi-square tests of proportions and logistic regression, with statistical significance criterion also set at $p < 0.05$. Zero-inflated negative binomial analyses will be used to contrast the study groups on count variables if warranted by a high percentage of zero alcohol use days over the follow-up (e.g., Agresti, 2002).

The principal power estimate focuses on categorical analyses since these will provide the most conservative power estimates and because we have somewhat more information available to estimate these outcomes for the Primary Aim study groups. (ES for continuous/count alcohol outcomes all demonstrated larger group effects than the categorical outcomes in the parent R01 [Kushner et al. 2013-a].) The best estimate for the categorical CBT-AR alcohol outcome comes from the PMRT group (also devoted exclusively to anxiety reduction) in the parent R01 (i.e., 53% relapse at four months). The parent R01 does not provide a point estimate for the CBT-DC group relapse rate but our prediction that the CBT-DC group will ameliorate all (or most) of the deleterious effect on recovery conferred by a co-occurring anxiety disorder allows us to place this estimate at 21%; i.e., the relapse rate at four months of an AUD treatment group with no co-occurring anxiety disorder (Kushner et al., 2005; also see Driessen et al., 2001 for similar estimates). These estimated results would represent a large effect size ($OR = 4.2$), which would require a sample of only 41 per group to identify an effect at an $\alpha = .05$ level with 80% power; however, a larger sample size would be required to identify other predicted effects with the same power. Further, we cannot be certain that our empirically- and theoretically-informed prediction that the CBT-DC will mitigate all/most of the risk for relapse conferred by co-occurring anxiety disorder is correct until the study is conducted. Therefore, we also calculated a minimum detectable ES showing that we could detect an OR as small as 2.3 with 80% power in the planned sample size using a two-tailed test and 0.05 alpha-level. Although we would be at a higher risk of missing effects even smaller than this, such negative findings would not constitute a meaningful Type II error because they would be of increasingly trivial clinical importance (e.g., Ferguson, 2009). **Therefore, the Primary Aim will be put to a meaningful and scientifically valid test under a wide range of clinically meaningful effect sizes.**

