4.3. Parent R01: Studies and Results

4.3.1. Recruitment. Over the four-year recruitment period for the RCT (Aim 2), we enrolled and randomized 344 cases. This works out to 86 randomized cases per year. In the final year of recruitment for the randomized study, we recruited 88 cases. In the no-cost extension period, we recruited 115 AUD TAU only cases. Based on this, we estimate we can typically recruit about 2 cases per week in the proposed work.

4.3.2. Retention. Over the life of the study, our retention rate was 78.5% (i.e., attrition was 21.5%) at the four-month follow-up. Our retention procedures improved significantly as indicated by an 87% retention rate in the final year (i.e., attrition about 13%). Based on this, we estimate a 75% retention rate in the proposed work.

[figure not shown]

4.3.2. Findings. As can be seen in the graphs, the alcohol outcomes obtained in the CBT group were superior to the other groups in all cases. The effects between the randomized groups (CBT vs. PMRT) were small for categorical outcomes (any drinking: $X^2 = 4.05$, $p = .04$, $d = .26$; and any three consecutive days drinking: $X^2 = 3.71$, $p = .05$, $d = .25$) and medium for count outcomes (drinks per month: $X^2 = 25.63$, $p < .001$, $d = .68$; drinking days per month ($X^2 = 10.23$, $p = .001$, $d = .42$; and number of binge days per month: $X^2 = 13.46$, $p < .001$, $d = .48$

[the latter is not shown in the graph]). These results support the key study hypothesis from Aim 2 of

the parent R01; i.e., that CBT would produce superior alcohol outcomes relative to a randomized active treatment control. They further demonstrate that the active treatment control, PMRT, did not significantly improve alcohol outcomes relative to TAU controls; however, since the TAU group was not randomized, caution must be taken when interpreting the latter findings. Although patient's "principal" anxiety disorder did not moderate these study results, level of BL anxiety was the only significant moderator; i.e., lower BL anxiety was associated with reduced CBT effects.

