6.0 STUDY PROCEDURES

6.1. Recruitment Strategy. Strategy: We will recruit individuals entering residential treatment for an alcohol use disorder at the Fairview Hospital Chemical Dependency program (Lodging Plus) for adults in Minneapolis. Participants will be recruited from the Consortium of Addiction Research (CAR) combined screening process, approved as IRB protocol #STUDY00005170. Complete details of the screening process can be found in the protocol for that study. Those who are eligible based on the CAR screening protocol will be invited to participate via the “1404S49427 Invite” and given a copy of the consent form. At the Baseline appointment they will have time to read the consent form and have their questions answered. In addition, they will watch a brief video of the study PI describing key elements of the study. If the staff person conducting the screening appointment is convinced the individual understands the consent form based on their answers to questions highlighting the key elements of participation, the individual will be offered the opportunity to sign the consent form. After signing the Consent Form, the baseline appointment will be completed and the appointments for the CBT therapy will be arranged.

Lodging Plus evaluates approximately 1000 chemically dependent patients per year, approximately 70% of whom are seeking treatment for alcohol dependence. Based on our experience in the parent R01 (see above), we should be able to recruit about two patients per week and a total of about 90-100 patients per year. Based on this, the target sample of 350 will be recruited in slightly less than 4 years. Our attrition rate over the entire life of the study was about 20% but was approximately 15% in the final year. (Note improvements in recruitment and retention over the course of the parent R01 reflects refined and improved methods based on our accumulating experience.) Based on the attrition estimate of 15%, we would have approximately 300 cases with four-month follow-up data, which will well power the study (see power estimates below).

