6.8.3. The Time Line Follow-Back (TLFB). The TLFB interview (Sobell & Sobell, 1995) will be used to identify daily drinking patterns of patients in the four months before treatment and in the intervals between study assessments. The TLFB has been shown to have adequate psychometric *qualities* in both clinical and non-clinical populations (Sobell & Sobell, 1995). Using a calendar, the respondent provides retrospective estimates of daily drinking over a specified amount of time. All primary and

secondary alcohol outcomes, with the exception of alcohol dependence from the SCID, will be derived from the TLFB assessment including: 1) any use vs. abstinence; 2) *percent or number (depending on the distribution) days drinking per month*; 3) *number of drinks per drinking day; and, 4) NIAAA-defined “hazardous drinking” (for men: > 4 drinks in a day or 14 drinks in a week; for women: > 3 drinks in a day or 7 drinks in a week) status.*

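### The primary population is all randomised patients, but the plan has no rule for missing 4-month relapse status and does not say whether a 1-month relapse counts, so the primary binary test defaults to complete cases

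*Combined protocol and SAP*

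**What the plan says.** Section 7.5 sets the population ("The primary intention to treat (ITT) population will include all patients randomized"), makes relapse yes/no one of the primary outcomes, and fixes the time point: "the primary assessment point will be the 4-month FU". For binary outcomes it says: "Categorical outcomes will be evaluated using chi-square tests of proportions and logistic regression". Just before that it names mixed models and GEE, chosen by whether residuals are normal, and remarks: "Both are flexible regression methods for incomplete repeated measures data". It adds that follow-ups "are keyed to the time since the last assessment".

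Section 6.8.3 has the Timeline Follow-Back (TLFB) collect daily drinking "in the intervals between study assessments", so drinking in the first month is on record for anyone seen at month 1.

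On loss to follow-up the documents give two planning figures. Section 6.1 uses 15% attrition, so that "we would have approximately 300 cases with four-month follow-up data". Section 4.3.2 says "we estimate a 75% retention rate in the proposed work", that is, 25% attrition, after reporting 21.5% over the parent trial and about 13% in its final year. Section 6.9 adds that patients who ask to terminate early are not contacted again.

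The general text on missing values (7.2, repeated in 8.2.2) provides for inspection. No section assigns a relapse status to a patient without a 4-month visit.

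**The concern.** Relapse yes/no at 4 months is the outcome behind the principal power estimate in 7.5. A chi-square or logistic analysis with no assignment rule drops every patient whose status is blank. The result is a comparison of patients who came back, reported under an ITT label.

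That matters because early drinking is a plausible reason for not returning. If relapsers are lost to a different degree in the two arms, the observed rates are pulled down unequally. The comparison is then biased, in a direction set by which arm loses more, and its type I error is no longer 5%.

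Some of this loss of information is avoidable. A patient who reports drinking at month 1 and is then lost has a known status if relapse means any drinking by month 4. If relapse covers only the period since the last visit, the status is not known. The plan does not choose. If the rule is left open, it could be settled after the blind is broken.

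**Working it through.** **1. The plan's own figure.** Inputs from 7.5: 53% v 21% relapse, two-sided alpha 0.05, 80% power. Pooled-variance formula, with mean rate 0.37:

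n' = [1.96 × √(2 × 0.37 × 0.63) + 0.842 × √(0.53 × 0.47 + 0.21 × 0.79)]² / 0.32² = 34.5.

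With continuity correction, n = (n'/4) × [1 + √(1 + 4/(n' × 0.32))]² = 40.5, so 41 per group, as stated. The 94 per group in 7.6 reproduces as 93.

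**2. How many are missing.** 350 × 0.15 = 52.5 and 350 × 0.25 = 87.5, about 53 to 88 patients. That leaves about 297 to 262, or 99.2 to 87.5 per arm. The planned 300 analysable cases (100 per group in 7.8) match the complete-case count at 15% loss, not the 350 randomised.

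**3. Complete-case power.**

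| Effect | 15% lost (99.2 per arm) | 25% lost (87.5 per arm) |
|---|---|---|
| 53% v 21% | 99.8% | 99.5% |
| OR 2.3 from 53% | 82.1% | 77.1% |

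At the planned effect, power is not the problem.

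**4. Bias when loss of relapsers differs by arm.** The documents give no dropout by arm or outcome, so these inputs are assumptions: equal true relapse of 53%, half of it by month 1 (26.5% early, 26.5% late, 47% none), early relapsers lost 40% in one arm and 15% in the other, everyone else lost 12%.

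- Arm losing 40%: (0.265 × 0.60 + 0.265 × 0.88) / (0.265 × 0.60 + 0.265 × 0.88 + 0.47 × 0.88) = 0.3922 / 0.8058 = 48.7%. Total loss 19%.
- Arm losing 15%: (0.265 × 0.85 + 0.265 × 0.88) / (0.265 × 0.85 + 0.265 × 0.88 + 0.47 × 0.88) = 0.4585 / 0.8721 = 52.6%. Total loss 13%.
- Spurious difference: 3.9 points. Starting from 41% relapse it is 3.7 points.

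Simulation with 117 per arm (at least 20,000 trials per scenario) gives a type I error of 8% to 9%. With 30% v 20% loss of early relapsers, the bias is about 1.5 points and the type I error stays under 6%. Swapping the arms reverses the sign.

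**5. What 1-month status recovers.** Same 40% v 15% scenario. The estimator counts relapses known at month 1 and applies the observed later relapse rate to the rest.

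| Share of lost patients seen at month 1 | Remaining bias under the null | Type I error |
|---|---|---|
| All | 0 points | about 5% |
| Half | about 1.7 points | about 6% |

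This estimator stands in for multiple imputation and is not identical to it. It also assumes that late relapse does not affect dropout.

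**6. Missing counted as relapse.** With missing share m, each rate becomes p(1 − m) + m. At m = 0.15, 53% v 21% becomes 60.1% v 32.9% (OR 3.07); at m = 0.25, 64.8% v 40.8% (OR 2.67). With all 350 kept, power is 98.9% and 96.1%. For a true OR of 2.3 the same rule gives 74.6% and 64.5%. It is therefore better as a sensitivity analysis than as the primary rule.

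**The case against.** A reader might infer that the plan restricts the test to completers and disregards 1-month relapses. It says neither. Counting missing as relapse, or imputing, would be equally compatible with 7.5. The complete-case reading rests on the absence of a rule and on the 300-case sizing.

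A reader might also infer that GEE is ruled out for relapse. It is not: 7.5 introduces mixed models and GEE for testing the hypotheses, including across all time points, and GEE can take binary data. But the choice between them turns on residual normality, and categorical outcomes then get their own tests, so coverage of relapse is unclear. Standard GEE would not in any case correct loss that depends on relapse.

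Nor does drinking in month 1 necessarily settle the outcome. If the 4-month status covers only the time since the last visit, it does not. Counting it defines the endpoint as well as handling missing data. Section 3.2 offers some support for the cumulative reading: it describes the 21% behind the CBT-DC planning rate as relapse within four months of treatment.

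The plan does have ways to limit loss. Section 6.9 encourages missed visits to be rescheduled and later ones attended, and an 8-month TLFB could fill in skipped days. That second route is closed to patients recruited after the modification described in 5.1, and neither route helps those who ask to terminate.

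Finally, the dropout patterns are assumed, milder ones do little harm, and recruiting 350 already budgets for 15% loss. All of this stands and limits the size of the point. It does not supply the missing rule.

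**Conclusion.** The point holds as a gap that conflicts with the stated ITT population. The primary binary test needs a status for all 350 patients, the plan gives no way to assign one to the 53 to 88 expected to lack it, and the relapse window is undefined. Followed as written, the test is a complete-case test.

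The size of any bias cannot be known from the documents. It depends on loss of relapsers differing by arm: about 3.8 points with type I error of 8% to 9% in the stronger assumed case, about 1.5 points and under 6% in the milder one.

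Two further inferences would go too far. The trial is not left underpowered at 53% v 21%; power is over 99% at either attrition figure, and the cost falls on smaller effects such as an OR of 2.3. And using 1-month data does not remove the bias altogether: if only half of those lost were seen at month 1, about 2 points remain.

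**What to change.** In section 7.5:

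1. Define the primary binary endpoint as any drinking from the end of study treatment to month 4, in line with the planning rate in 3.2, and count drinking recorded at any visit within that window as relapse.
2. For statuses still missing, multiply impute by arm using available TLFB data, baseline drinking and the trait-anxiety stratum, and run the logistic test on all randomised patients.
3. Report missing-equals-relapse and arm-specific delta analyses as sensitivity analyses. These cover patients not seen at month 1 and dropout that the imputation model does not explain.
4. Reconcile the 15% attrition in 6.1 with the 25% implied in 4.3.2.

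The cost is a few sentences and modest extra analysis; every variable named is already collected. The one substantive decision is the endpoint window, which should be made explicitly and before the blind is broken.
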